6.4.2 Secondary Efficacy Variables

The best overall response is defined as the best visit response recorded from the start of the treatment until disease progression/recurrence. This data will be summarized using frequency and percentage for

CONFIDENTIAL Document Date: 12MAY2023. ST-AD-032 version 01

Complete Response (CR), Partial Response (PR), Stable Disease (SD), and Progressive Disease (PD) for each treatment group.

- Overall Response Rate (ORR): The percentages of CR+PR will be calculated and presented along with 95% confidence intervals of these percentages.
- Clinical Benefit Rate (CBR): The percentages of CR+PR+SD>=24 weeks will be calculated and presented along with 95% confidence intervals of these percentages.
- Progression Free Survival (PFS): It is defined as time from the first dose of study drug to documented disease progression or death due to any cause. This variable will be analyzed via Kaplan-Meier methodology.

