8 ASSESSMENT OF EFFICACY

8.1 Specification of the Efficacy Parameters

Initial disease assessment of patients should be performed within 28 days prior to the first dose of study drug using computed tomography (CT) and/or magnetic resonance imaging (MRI). This scan will be considered as baseline scan. The PI should review baseline scan images to confirm the subject has measurable disease as defined in the inclusion criteria. Scan performed as part of routine clinical management is acceptable for use as the baseline scan if it is of diagnostic quality and performed within 28 days prior to the C1D1, or as approved by the medical monitor if it is out of window period.

Subsequent scan (CT and/or MRI as applicable) should be done at C3D1 (± 7 days) and approximately 8 weeks thereafter (± 7 days), and/ or at the EOT and so on or as clinically indicated (if clinical progression is suspected). If a CR or PR is noted, confirmatory scans should be performed at least 4 weeks after the initial response was first documented. The scan should be reviewed by site investigator/radiologist/designee and tumour response will be assessed according to the revised Response Evaluation Criteria in Solid Tumour guideline (RECIST) version 1.1.[21]

8.2 Images included in the assessment.

A CT with IV contrast will be the primary modality for assessment, unless the patient has an allergy to contrast that cannot be controlled with pre-medications. If patients are unable to receive iodinated CT contrast, the preferred imaging is non-contrast CT of the chest, and MRI of the abdomen and pelvis with contrast. Tumour imaging should remain consistent throughout study and should include those thought by investigator to best capture status of disease. For skin nodules, CT or MRI will be the preferred modality of assessment. Digital photography will not be acceptable as a method of assessment for skin lesions.

8.3 Measurable and non-measurable disease:

Eligibility of lesions for quantitative assessment will be determined at baseline, with target lesions selected from the measurable lesions identified. After baseline, target lesions will always be assessed quantitatively, and non-target lesions will be assessed qualitatively, with no further evaluation of measurability according to these definitions.

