New lesion response is classified as present or not ("Yes" or "No"). The response is "Yes" if there is at least one lesion that the investigator considers unequivocal new tumour.

CONFIDENTIAL Page 52 of 66

- Lesions that are equivocal (for example, due to small size) should not be considered new until they are confirmed by later scanning. Once confirmed, they can be retrospectively called new lesions at the time they were first seen.
- A lesion identified in an area not previously scanned is considered a new lesion.
- New lesions seen on nuclear medicine bone scans should be confirmed using anatomical imaging, whenever possible. If bone lesions are confirmed on later CT or MRI scan, progression should be assigned to the visit in which new lesion(s) were first seen on bone scan (in a manner similar to other equivocal new lesions). In the absence of structural confirmation, the pattern of lesions must clearly indicate metastasis, usually with at least two new lesions present.

Overall response is determined by combining the target, non-target, and new lesion responses.

| Table 9 | : | Response | Assessment |
|---------|---|----------|-------------------|
|---------|---|----------|-------------------|

| Target Lesions | Non-Target Lesions | New Lesions | Overall Visit Response |
|-----------------------|---------------------|-------------|---------------------------|
| CR | CR | No | CR |
| CR | Non-CR/Non-PD or NE | No | PR |
| PR | Non-CR/Non-PD or NE | No | PR |
| SD | Non-CR/Non-PD or NE | No | SD |
| PD | Any | Yes or No | PD |
| Any | PD | Yes or No | PD |
| Any | Any | Yes | PD |

After all visits have been evaluated, the sequence of overall visit responses is used to derive best overall response (BOR).

- BOR is defined as the best visit response recorded from the start of the treatment until disease progression/recurrence.
- ORR: It is defined as sum of CR and PR rates
- Clinical Benefit Rates: It is defined as sum of CR, PR and SD rates
- PFS is measured from the time of first dose of study drug to radiographic (or tumour marker as applicable) documentation of disease progression or death due to any cause.

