8.7.2 Analysis of Secondary Efficacy Variables

These secondary efficacy variables will be analysed and summarised to evaluate safety and tolerability of tenalisib.

• Overall Response Rate (ORR): It is defined as sum of CR and PR rates.

The percentages of CR+PR will be calculated and presented along with 95% confidence intervals of these percentages.

This data will be summarized using frequency, and percentage along with 95% confidence intervals of these percentages using exact method based on binomial distribution.

The corresponding listing will also be provided.

• Clinical Benefit Rate (CBR): It is defined as sum of CR, PR and SD at 24 weeks or longer.

The percentages of CR+PR+SD>=24 weeks will be calculated and presented along with 95% confidence intervals of these percentages.

This data will be summarized using frequency, and percentage along with 95% confidence intervals of these percentages using exact method based on binomial distribution.

The corresponding listing will also be provided.

Progression Free Survival (PFS): It is defined as time from the first dose of study drug to
documented disease progression or death due to any cause.
 PFS is measured from the time of first dose of study drug to radiographic (or tumour marker as
applicable) documentation of disease progression or death due to any cause. Patients who did not
progress or die will be censored on the last date the patient is known to be radiologically
progression free. The summary table for PFS rate at 6-Month and 1-year by metastasis type will
also be provided.

This variable will be analyzed via Kaplan-Meier methodology and displayed graphically for each treatment group and overall. The following reports will be generated:

- The Q1, median and Q3 PFS time will be provided. The 95% CI for the Q1, median, and Q3 PFS time will be presented for each treatment group and metastasis group using Brookmeyer-Crowley method.
- The number and % of patients with disease progressive events (further divided into progression or death) will be provided.
- The number and % of patients censored (further divided by reasons for censoring) will be provided.
- Kaplan-Meier curves will be produced.
- · A listing of PFS data will be provided.

Additional efficacy variables

Duration of Treatment: Duration of treatment is defined as the time from first dose to last dose of drug.

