Page 42 of 106 ST-AD-032 version 01 Page xx of yy

* The 95% CIs are reported using exact method based on binomial distribution.

The BOR is defined as the best visit response recorded from the start of the treatment until disease progression/recurrence. The response rates (CR/ PR/ SD/SD>=24 weeks/PD) are estimated using (BOR) recorded in each patient. For the patients without any post-baseline efficacy assessment, BOR is considered as 'Not evaluated'.

For SD \geq 24 weeks, patients with treatment duration \geq 168 (\pm 7) days are summarized.

CR- Complete Response; PR- Partial Response; SD- Stable Disease; PD- Progressive Disease; ORR- Objective Response Rate; CBR- Clinical Benefit Rate. Reference Listing 16.2.x.x

Program: xx.sas Table Generation: ddmmmyyyy hh:mm:ss

Use same format for

Document Date: 12MAY2023.

1. Table 14.2.2.2 Summary of Objective Response Rate and Clinical Benefit Rate by type of metastasis – ITT Analysis Set <Column 1: same as table 14.2.2.1; Column 2: de novo metastasis; Column 3: recurrent metastasis; Column 4: Overall>

2. Table 14.2.2.3 Summary of Objective Response Rate and Clinical Benefit Rate – Per Protocol Analysis

CONFIDENTIAL Page 43 of 106 ST-AD-032 version 01

Protocol RP6530-2101 Table 14.2.3.1 Summary of Progression Free Survival ITT Analysis Set Page xx of yy

	Tenalisib 800 mg BID	Tenalisib 1200 mg BID	Overall
	(N=xx)	(N=xx)	(N=xx)
Number (%) of patients with Progressive Disease/Death	xx (xx.x)	xx (xx.x)	xx (xx.x)
Progressive Disease, n (%)	xx (xx.x)	xx (xx.x)	xx (xx.x)
Death, n (%)	xx (xx.x)	xx (xx.x)	xx (xx.x)
Number (%) of censored patients	xx (xx.x)	xx (xx.x)	xx (xx.x)
Reason for Censoring n(%)			
XXXXXXXXXXXXXX	xx (xx.x)	xx (xx.x)	xx (xx.x)
xxxxxxxxxxxxx	xx (xx.x)	xx (xx.x)	xx (xx.x)
Time to Progressive Disease/ Death (days)			
Quartiles (95% CI)*			
Q1	xx.x(xx.x, xx.x)	xx.x(xx.x, xx.x)	xx.x(xx.x, xx.x)
Median	xx.x(xx.x, xx.x)	xx.x(xx.x, xx.x)	xx.x(xx.x, xx.x)
Q3	xx.x (xx.x, xx.x)	xx.x (xx.x, xx.x)	xx.x (xx.x, xx.x)
Range (min, max)	(xx, xx)	(xx, xx)	(xx, xx)

The ITT analysis set includes data from all patients who received at least 1 dose of study medication.

Percentages are based on the total number of patients (N) in each treatment group.

CONFIDENTIAL

Page 44 of 106 ST-AD-032 version 01

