Program: xx.sas Listing Generation: ddmmmyyyy hh:mm:ss

Page 77 of 106 ST-AD-032 version 01

Protocol RP6530-2101 Listing 16.2.6.1

Cancer Assessment

All Patients

Page xx of yy

Patient ID	Treatment Group	Type of Metastasis	ITT/PP	Visit	Assessment performed/Date of Assessment	Reason if assessment not performed	Lesion site	Presence of lesion	Number/Location of Lesion within site	Site name/ Number of Lesion within other site or soft tissue)
xxxx Repeat f	Xxxxxx for all the sites	XXXXXX	Yes/Yes	Screening	Yes/DDMMMYYYY	XXXXX	Breast Lymph nodes Lung Liver Bone Other soft tissue	Yes No No	1	

EOT: End of Treatment

Document Date: 12MAY2023.

Program: xx.sas Listing Generation: ddmmmyyyy hh:mm:ss

Page 78 of 106 ST-AD-032 version 01

Protocol RP6530-2101 Listing 16.2.6.2 Target Lesion Assessment All Patients

Document Date: 12MAY2023.

Page xx of yy

PatientT	Treatmer	nt ITT/PP	Number of	Visit	Assessment Performed/	Evaluation	Lesion	Tumor Sum	% Change	>0.5cm
ID (Group	Type of	Measurable		Date of Assessment	Method	Number/	Laterality/ of lesi	on from Nadir/	Absolute
		metastasis	Lesions/				Anatomical	Lesion diame	ters % Change	Increase in
			Target Lesions				Location	Diameter	in SLD from	Any Lesion
			at Screening					(cm)	Baseline#	Size/
										Overall
										Response
										of Target
										Lesions
Xxxx X	Xxxxxx	xxxxxxxx Yes/Yes	x/x	Screening	Yes/DDMMMYYYY	CT	1/xxxxxx	Left/xx.x xx.x	xx.x/xx.x	Xx/xx
						CT	1/xxxxxx			
		Yes/Yes	xx/xx	Cycle 3 Day1	Yes/DDMMMYYYY	CT	1/xxxxxx	Left/xx.x xx.x	xx.x/xx.xx	Xx/xx

ITT: Intent-To-Treat Analysis Set, PP: Per Protocol Analysis Set, EOT: End of Treatment, SLD: Sum of Lesion Diameter #((SLD at Visit – SLD at Screening)/SLD at Screening)x100

Program: xx.sas Listing Generation: ddmmmyyyy hh:mm:ss

Page 79 of 106 ST-AD-032 version 01

Protocol RP6530-2101 Listing 16.2.6.3 Non-Target Lesion Assessment All Patients Page xx of yy

Patient ID	Treatment Group	Type of metastasis	ITT/PP	Non- target Lesion at screening	Visit	Was Assessment Performed? Date of Assessment	Non-target Lesion Complete Resolved?	Evaluation Method	Lesion Number/ Anatomical Location	Tumor Laterality	Lesion Present at Screening	Any unequivocal increase in lesion	Overall Response of Non- Target Lesions
xxxx	Xxxxx	xxxxxx	Yes/Yes	Yes	Screening	Yes/ DDMMMYYYY	No	CT	1/xxxx	Right	No	No	xxxxx
xxxx	Xxxxx	xxxxx	Yes/Yes	Yes	Cycle 3 Day 1	Yes/ DDMMMYYYY	No	CT	1/xxxx	Left	No	No	xxxxxxx

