ITT: Intent-To-Treat Analysis Set, PP: Per Protocol Analysis Set, EOT: End of Treatment

Program: xx.sas Listing Generation: ddmmmyyyy hh:mm:ss

Document Date: 12MAY2023.

Protocol RP6530-2101 Listing 16.2.6.4 Overall Tumor assessment ITT Analysis Set

Document Date: 12MAY2023.

Page xx of yy

Patient ID	Treatment Group	Type of metastasis	PP	Visit	Overall tumor assessment performed?	If No, reason	Overall assessment date	Overall Response	If progressive disease, date of first radiological evidence of progression
xxxx	Xxxx	Xxxxx	Yes	xxxx	Yes		DDMMMYYYY	Xxxxx	DDMMMYYYY
XXXX	Xxxxx	XXXXX	Yes	XXXX	Yes		DDMMMYYYY	xxxxx	
XXXX	Xxxxx	XXXXX		XXXX	Yes		DDMMMYYYY	xxxxx	
xxxx	Xxxxx	xxxxx		xxxx	No	xxx			

ITT: Intent-To-Treat Analysis Set, PP: Per Protocol Analysis Set, EOT: End of Treatment

Program: xx.sas Listing Generation: ddmmmyyyy hh:mm:ss

Protocol RP6530-2101 Listing 16.2.6.5 New lesion assessment ITT Analysis Set Page xx of yy

Patient ID	Treatment Group	Type of metastasis	PP	Visit	Any New Lesion?	Date of Detecting New Lesion	Number of new lesions	New lesion site	Method of assessment	
Xxxx	Xxxx	XXXX	Yes	XXXX	Yes	DDMMMYYYY	Xx	XXX	Xxxx	XX
Xxxx	Xxxxx	xxxxx	Yes	XXXX	Yes	DDMMMYYYY	Xx	XXX	Xxxx	xx
Xxxx	Xxxxxx	xxxxxx	Yes	XXXX	Yes	DDMMMYYYY	Xx	XXXX	Xxxx	
Xxxx	Xxxxx	xxxxxx	Yes	XXXX	No					
Xxxx	Xxxxx	xxxxxx	Yes	xxxx	Yes	DDMMMYYYY	XX	XXX	Xxxx	
Xxxx	Xxxxx	xxxxxx	Yes	xxxx	No					

ITT: Intent-To-Treat Analysis Set, PP: Per Protocol Analysis Set, EOT: End of Treatment

Program: xx.sas Listing Generation: ddmmmyyyy hh:mm:ss

Protocol RP6530-1802

Page xx of yy

Listing 16.2.6.6 Visit Wise Response ITT Analysis Set

Patient ID	Treatment Group	Type of Metastasis	PP	C3D1	C5D1	C7D1	C9D1	C11D1	C13D1	l C15D1	C17D	1 C19D1	ЕОТ	BOR	DOT(in Days)	DOR (in Days)	Best Change from baseline
XXXX	Xxxx	Xxxxxxxx	Yes	XX	XX	XX	XX	XX	XX	XX	XX	XX	XX	XX	Xx	Xx	Xxxxx
XXXX	Xxxx	Xxxxxxx	Yes	XX	XX	XX	XX	XX	XX	XX	XX	XX	XX	XX	Xx	Xx	Xxxxx
XXXX	Xxxx	Xxxxxxxx	Yes	XX	XX	XX	XX	XX	XX	XX	XX	XX	XX	XX	Xx	Xx	Xxxxx
XXXX	Xxxx	Xxxxxxx	Yes	XX	XX	XX	XX	XX	XX	XX	XX	XX	XX	XX	Xx	Xx	Xxxxxx
XXXX	Xxxx	Xxxxxxx	Yes	XX	XX	XX	XX	XX	XX	XX	XX	XX	XX	XX	XX	XX	Xxxxxx
xxxx	Xxxx	xxxxxxxx	Yes	XX	XX	XX	XX	XX	XX	XX	XX	XX	XX	XX	XX	XX	xxxxxx

The BOR is defined as the best visit response recorded from the start of the treatment until disease progression/recurrence. For the patients without any post-baseline efficacy assessment, BOR is considered as 'Not evaluated'.

Duration of Treatment (DOT) = Date of Last Dose - Date of First Dose + 1.

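### Confirmatory scans are requested after a CR or PR, but ORR, CBR and DoR count the best single visit, and no supportive confirmed ORR is tabulated

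*SAP*

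**What the plan says.** **The scan.** Protocol 8.1 says: "If a CR or PR is noted, confirmatory scans should be performed at least 4 weeks after the initial response was first documented". Footnote 15 of the schedule of events repeats this in both the protocol (Table 5) and the SAP (6.1).

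**The response definition.** Protocol 8.5 says "BOR is defined as the best visit response recorded from the start of the treatment until disease progression/recurrence" and defines ORR as CR plus PR. SAP 6.4.2 carries the same rule: "The best overall response is defined as the best visit response recorded from the start of the treatment until disease progression/recurrence". The footnote to Table 14.2.2.1 (SAP Section 12) repeats it and derives the response rates from that BOR. Neither document attaches a confirmation condition.

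**The analysis.** For ORR and CBR, SAP 8.7.2 says: "This data will be summarized using frequency, and percentage along with 95% confidence intervals of these percentages using exact method based on binomial distribution". Table 14.2.2.1 has rows for CR, PR, SD, SD of at least 24 weeks, PD, not evaluated, ORR and CBR. None refers to confirmation. DoR (SAP 6.4.3 and 8.7.2) runs from the first occurrence of a CR or PR.

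**The listings.** Listing 16.2.6.2 gives dated sums of diameters and Listing 16.2.6.4 gives dated overall responses. Listing 16.2.6.6 gives responses at the odd-cycle visits and EOT, with BOR and DoR. It has no confirmation flag and no column for an unscheduled scan.

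**The concern.** The plan calls a scan confirmatory but never says what its result decides. A patient with PR at C3D1 and PD at C5D1 has failed confirmation, yet remains a responder. The same patient counts as clinical benefit, although a patient whose best response is SD must hold it for 24 weeks to count. The patient also enters DoR from the C3D1 scan.

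Response is read by the site investigator (protocol synopsis) in an open-label study (SAP 4.4), and the study is meant to help choose between two doses on a signal of efficacy with acceptable safety (protocol 1.5.2). In that setting it is useful to know how many responses persisted. As planned, any gap between best-visit and confirmed ORR is not tabulated, although the scans that would show it are already scheduled.

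**Working it through.** The plan states no assumed ORR or confirmation rate, so there is no ORR figure to reproduce. Its one design figure (13% precision, protocol 9.2) concerns the primary endpoint and does not bear on this point.

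**1. Direction.** Every confirmed responder is also a best-visit responder, so best-visit ORR ≥ confirmed ORR. The two are equal if every response is confirmed.

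**2. Size per patient.** Inputs: 20 per group and 40 in total (protocol 9.2), assuming all are dosed and so in the ITT set.
- One group: 1/20 = 5.0 points.
- Overall column: 1/40 = 2.5 points.

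**3. Illustration.** Assume 4 best-visit responders in a group of 20; the documents give no count. The exact (Clopper-Pearson) 95% limits for x of n are the 0.025 quantile of Beta(x, n−x+1) and the 0.975 quantile of Beta(x+1, n−x).

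| Not confirmed | Confirmed ORR | Exact 95% CI |
|---|---|---|
| 0 | 4/20 = 20% | 5.7% to 43.7% |
| 1 | 3/20 = 15% | 3.2% to 37.9% |
| 2 | 2/20 = 10% | 1.2% to 31.7% |

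The intervals overlap widely. What is gained is transparency, not a sharper comparison of doses.

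**4. Are the scans already there?** Inputs: 28-day cycles, and 8-weekly scans with ±7-day windows (footnotes 15 and 20).
- C3D1 is day 2×28+1 = 57, C5D1 is day 4×28+1 = 113 and C7D1 is day 6×28+1 = 169.
- Gap between consecutive odd-cycle scans: 113−57 = 56 days. With ±7 days at both ends it is 56−14 = 42 to 56+14 = 70 days, always above 28.
- Exception A, a response first seen on an unscheduled scan. Taking day 90 as an example, the C5D1 window is days 106 to 120, so the gap is 16 to 30 days and may be under 28.
- Exception B, C25 to C26, since footnote 20 ends its example at C26. C25D1 is day 24×28+1 = 673 and C26D1 is day 25×28+1 = 701. The gap is 28 days, or 14 to 42 with the windows.

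A rule that requires an assessment at least 28 days later, rather than simply the next scan, handles both exceptions.

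**5. Reach beyond ORR.** In the C3D1 PR, C5D1 PD example, the patient adds one to the CBR count and contributes a DoR of about 113−57 = 56 days. CBR does not always change: a PR that reverts to SD could still qualify if SD lasts 24 weeks.

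**The case against.** The strongest reply is that this is a preference. The protocol itself defines BOR as the best visit response, the SAP copies that faithfully, and the table footnote discloses it. The scan is something that should be done, and neither document says that an unconfirmed response is not a response. All of this stands. A reader might infer that the SAP departs from the protocol or breaches a promised endpoint; the documents do not support that, because neither promises a confirmed ORR.

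Nor is the confirmatory scan wasted. It feeds PFS, DoR and the tumour plots. A response followed by early progression would appear as a short duration in the DoR table. With at most about 40 patients, persistence can be pieced together from Listings 16.2.6.2, 16.2.6.4 and 16.2.6.6. That also stands, but it is work by hand across several listings, and a PR that reverts to SD does not show in DoR.

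The dose-selection argument is limited as well. Counting unconfirmed responses would distort the choice of dose only if they fell unevenly between the groups, and nothing in the documents suggests that they will. Dose choice also rests on safety.

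Finally, a definition added to a SAP dated 12 May 2023, which already records early closure (SAP 5.1), comes late in an open-label study. Declaring it does not remove that limitation, so the added row must stay supportive.

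What survives is that the protocol collects data to verify response and the stated rule then ignores them when counting responders.

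**Conclusion.** The point holds as a cheap improvement. A CR or PR that fails its confirmatory scan still counts in ORR, CBR and DoR, and no output shows how many do. The effect on ORR is 5 points per such responder in a group of 20 and 2.5 points in 40, assuming all planned patients are dosed. The number of such responders is unknown and may be zero.

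Two stronger readings should be resisted. One is that the reported ORR will be inflated: the documents show only that it cannot fall below the confirmed rate. The other is that every next scheduled scan satisfies the 4-week minimum: this is true between consecutive odd-cycle scans, but not necessarily after an unscheduled scan or between C25 and C26.

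Importance is modest. ORR is secondary, with no hypothesis or threshold. The primary endpoint, the percentage without progression at 6 months, does not use BOR.

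**What to change.** In SAP 6.4.2, SAP 8.7.2 and ITT Table 14.2.2.1 only:

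1. Keep the protocol-defined ORR as the headline, labelled *best visit response, confirmation not required*.
2. Add one supportive confirmed-ORR row with an exact 95% CI. Count a CR or PR as confirmed only if CR or PR is also recorded at an assessment at least 28 days after it was first documented and before progression.
3. State in advance how these are classed: CR then PR, PR-SD-PR, a non-evaluable scan, and progression within 28 days.
4. Among responders not confirmed, show *failed confirmation* and *no later scan at least 28 days on* separately. The second covers a response first seen at the last scan, an EOT scan omitted because one was done within 28 days (protocol 6.8), and early closure (SAP 5.1).
5. Add a confirmation flag to Listing 16.2.6.6.
6. Note under the table that CBR and DoR use best-visit responders, so the confirmed row is not read as sharing their responder set.
7. Declare the addition in SAP 5.2 as supportive and made after early closure.

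**Cost.** One derived flag, one rate row, two count rows, one listing column, a footnote and a line in SAP 5.2. There are no new scans and no change to the protocol 8.5 definition, and the row need not be repeated in the per-protocol or metastasis-type tables. The downside is that the supportive figure may be lower, and responses first seen at the last scan cannot be confirmed, which is why they have their own category.

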6.4.3 Additional Efficacy Variables

Duration of Treatment Exposure: Duration of treatment exposure is defined as the time from first dose to last dose of drug.

Duration of Response: Duration of response (DoR) is defined as the time from the first occurrence of partial or complete response to disease progression or death in patients who achieve complete or partial response. For patients who neither progress nor die, the duration of response will be censored on the last date the patient is known to be radiologically progression free.

Duration of clinical benefit: Duration of clinical benefit (DoCB) is defined as the time from the first dose of study drug to disease progression or death in patients who achieve complete response, partial response, or stable disease for 24 weeks or longer. For patients who neither progress nor die, the duration of response will be censored on the last date the patient is known to be radiologically progression free.

Proportion of patients with 6-Month and 1-year PFS.

PFS rate at 6-months or at 1-year: Proportion of patients who remained alive and progression-free at 6 months or at 1-Year

